3.4.7.2 Analyses of HbA_{1c}

 HbA_{1c} parameter will be summarized on the safety population by analysis visit using number of available data, mean, SD, median, minimum, and maximum for each treatment during the treatment period. Summary will be also provided according to the diabetes mellitus status at baseline (see Section 3.1.1). The time profile will be plotted by treatment group with the means and the corresponding standard errors (SEs).

In case the proportion of initiation of anti-diabetic medications is different between the 2 treatment groups, further analysis of HbA_{1c} over time would be performed.

3.4.7.3 Analyses of patients with LDL-C <25 mg/dL(<0.65 mmol/L)

The number and percentage of patients with 2 consecutive LDL-C <25 mg/dL (respectively, LDL-C <15 mg/dL, ie, 0.39 mmol/L) will be provided by treatment group on the safety population. Kaplan-Meir curves will be provided for the time to the first LDL-C <25 mg/dL (respectively 15 mg/dL) for these patients. For this analysis, patients without post-baseline LDL-C result or with only 1 post-baseline LDL-C result will not be included.

3.4.7.4 Analyses of lipid parameters

The lipids variables (see Section 3.1.5.1) will be analyzed using an ITT approach (based on the ITT population) including all lipid values, regardless of whether the patient was continuing therapy or not. In addition, analyses will also be conducted using an on-treatment approach (based on the randomized and treated population) only including lipid data collected during the treatment period.

3.4.7.4.1 ITT analyses

A pattern-mixture model approach (see Appendix F) will be used with a different imputation strategy applied for missing lipid values during the treatment period (ie, within the time period from the first double-blind IMP injection up to the day of the last double-blind injection +21 days) and missing lipid values after treatment discontinuation (ie, after the day of last injection +21 days) based on the following assumptions:

- Patients within 21 days of their last double-blind IMP injection would continue to show benefit from treatment similar to that observed at the scheduled time point. Therefore, lipid values missing during the treatment period (samples obtained outside the specified window, no blood sample available although visit was performed, etc) should be considered "Missing At Random" and imputed based on other on-treatment measurements;
- Patients who stopped taking their study treatment no longer benefited from it after discontinuation and thus tended to have lipid values returning to baseline. Thus lipid values missing after treatment discontinuation will be imputed based on patient's own baseline value.

Missing lipid values will be imputed 10 times using the MI SAS® procedure, to generate 10 complete data sets. The percent change from baseline and/or the absolute change from baseline at a pre-specified time point will be derived from observed and imputed lipid value at this time point. Imputed values for time points after CSED will be discarded.

TGs and Lp (a) data will be log-transformed before imputation process and then back-transformed to create the imputed data sets.

The completed data sets will be analyzed using an analysis of covariance (ANCOVA) model for continuous lipid variables other than Lp (a) and TGs or a robust regression (6) model for Lp (a) and TGs continuous variables with treatment group as fixed effect, and the baseline lipid value as continuous covariate. The MIANALYZE procedure will be used to generate valid statistical inferences by combining results from the 10 analyses using Rubin's formula.

The number of imputations (10) will be informally verified by replicating sets of 10 imputations and checking whether the combined results are stable. If not stable, the number of imputations will be increased and informally checked as above, and thus until stable estimates are obtained.

The value at the CSED will be the value obtained at the CSED visit. For patients without CSED visit, the last lipid value observed or imputed up to CSED will be taken into account.

Throughout the ANCOVA and robust regression models, the alirocumab group will be compared to placebo using appropriate contrasts tested at the two-sided 0.05 level, and providing the 95% CI of the difference, for the different time points as well as at the CSED.

No adjustment will be made for lipid variables for which p-values will be provided for descriptive purpose.

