### **10.3 HANDLING OF PATIENT TEMPORARY OR PERMANENT TREATMENT DISCONTINUATION AND OF PATIENT STUDY DISCONTINUATION**

All randomized patients should be treated with blinded study treatment (IMP) for as long as possible.

As a general rule, any IMP treatment discontinuation should be initially considered temporary, and Investigator should make best effort to resume IMP treatment as early as practically possible, after several weeks or months (pending there are no safety concerns), and perform all study visits and assessments as usual.

Permanent IMP discontinuation should be a last resort. Any IMP discontinuation should be fully documented in the eCRF and source notes.

Pregnancy will lead to permanent treatment discontinuation in all cases.

All randomized patients should be followed-up (and suspected efficacy endpoints collected) until the end of the study (common study end date visit), even if treatment was permanently discontinued early.

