3.1.4 Safety endpoints

Following injections are considered as double-blind IMP injections:

• For patients randomized in the placebo group: any injection from double-blind kits;

• For patients randomized in the alirocumab group: any injection from double-blind kits excepted placebo injections given to maintain the blind in case of 2 consecutive LDL-C values <15 mg/dL.

Of note potential additional training injections after randomization using training injection kits will not be taken into account.

The period of safety observation starts from the time when the patient gives informed consent and is divided into three periods:

- PRE-TREATMENT period: defined from the signed informed consent up to the first dose of double-blind IMP injection;
- Treatment-emergent adverse event (TEAE) period: defined as the time from the first dose of double-blind IMP injection to the last dose of double-blind IMP injection +70 days (10 weeks), (as residual effect of treatment is expected until 10 weeks after the stop of double-blind IMP).

The TEAE period will include:

- The TREATMENT period defined as the time from the first dose of double-blind IMP up to the day of last dose of double-blind IMP injection +21 days, as serum concentration of alirocumab >10 μ g/mL is expected for approximately 21 days following administration of 150 mg, and because throughout the previous studies it was observed that when alirocumab concentrations declined below this concentration, decrease in effect on LDL-C is observed.
- The RESIDUAL TREATMENT defined as the time from the day of last dose of double-blind IMP injection +22 days up to the day of last dose of double-blind IMP injection +70 days (10 weeks).
- POST-TREATMENT period: defined as the time starting the day after the end of the TEAE period.

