3.4.7.4.2 On-treatment analyses

Analysis of lipid variables will be conducted during the treatment period. Post-treatment data will not be considered.

The lipid variables other than Lp (a) and TGs will be analyzed in the randomized and treated population using a mixed-effect model with repeated measures (MMRM) approach. All post-baseline on-treatment data available within Month 1 to Month 64 analysis windows will be used and missing data will be accounted for by the MMRM model.

The model will include the fixed categorical effects of treatment group (placebo, alirocumab), planned time point (Month 1 to Month 64), treatment-by-time point interaction, as well as, the continuous fixed covariate of baseline lipid value and baseline lipid value-by-time point interaction. This model will be run using SAS Mixed procedure with an unstructured correlation matrix to model the within-patient errors. Parameters will be estimated using restricted maximum likelihood method with the Newton-Raphson algorithm. Denominator degrees of freedom will be estimated using Satterthwaite's approximation. This model will provide baseline adjusted least-squares means estimates over time for both treatment groups with their corresponding SEs and 95% CI. To compare the alirocumab group to the placebo group, appropriate contrasts statement will be used to test the differences of these estimates, at the 2-sided 0.05 level, for the different time points.

Note: in case of computation issue for this approach, multiple imputation under missing-at-random (MAR) assumption will be conducted, followed by an ANCOVA model.

The Lp (a) and TGs will be analyzed in the randomized and treated population using multiple imputation (same imputations as in Section 3.4.7.4.1 without discarding imputations of missing values during the post-treatment period (see Appendix F).

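### Lipid values missing during treatment interruptions longer than 21 days are imputed as if the patient were still on drug

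*SAP*

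**What the plan says.** SAP 3.4.7.4.1 sorts missing lipid values into two classes.

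- **During the treatment period**, meaning "within the time period from the first double-blind IMP injection up to the day of the last double-blind injection +21 days". These values are taken as missing at random and "imputed based on other on-treatment measurements".
- **After that date.** Here "lipid values missing after treatment discontinuation will be imputed based on patient's own baseline value".

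The reason given for the first class is that "Patients within 21 days of their last double-blind IMP injection would continue to show benefit from treatment". SAP 3.1.4 defines the treatment period over the same span ("defined as the time from the first dose of double-blind IMP up to the day of last dose of double-blind IMP injection +21 days") and explains the 21 days. Serum concentration is expected to stay above a stated level for roughly that long after 150 mg, and "when alirocumab concentrations declined below this concentration, decrease in effect on LDL-C is observed".

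Protocol 10.3 tells sites to regard any stop as temporary at first and to "resume IMP treatment as early as practically possible, after several weeks or months". Protocol 10.3.3 encourages restart with no limit on how long the stop has lasted, and 10.3.1 counts even one omitted injection as an interruption.

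The on-treatment analysis in SAP 3.4.7.4.2 uses the same span: "Analysis of lipid variables will be conducted during the treatment period".

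**The concern.** The 21-day argument concerns time since an injection, whichever injection that is. The rule uses it only for the last one. A patient on day 60 of a 90-day gap is therefore inside the treatment period whenever a further injection follows, although the SAP's own reasoning no longer supports an on-drug value.

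Take two alirocumab patients who have been off drug equally long and miss the same sample. If one later restarts, the missing value is imputed from on-treatment data. If the other never restarts, it is imputed from baseline. The class depends on a later event, not on the patient's state at the time point.

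At stake is the ITT estimate of the lipid effect, which SAP 1.2.2 lists as a secondary objective. An imputed value can also become the end-of-study value, because 3.4.7.4.1 uses the last observed or imputed value for patients without a common study end date visit.

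**Working it through.** The plan states no figure on this point, so there is nothing to reproduce. The check compares the texts and then sets a scale.

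**Step 1. Does any text exclude gaps?** SAP 3.1.4 and 3.4.7.4.1 both run without a break from first to last injection plus 21 days. SAP 3.4.3.1 mentions intermittent discontinuations only to say that exposure duration and the dose-level summaries ignore them. The examples of missingness in 3.4.7.4.1 are samples outside the window and visits without a blood sample; neither describes a patient off drug. Appendix F, cited for the detail of the model, was not in the text available.

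**Step 2. How much of a gap lies beyond the SAP's own limit?** For G days between two successive injections, the share beyond day 21 is (G − 21)/G.

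| G (days) | Days beyond 21 | Share |
|---|---|---|
| 28 (one injection omitted) | 7 | 25% |
| 56 | 35 | 63% |
| 91 | 70 | 77% |
| 183 | 162 | 89% |

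The current rule counts all of these days as on-treatment if another injection follows.

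**Step 3. Upper bound on the bias in the LDL-C difference.** Bias ≤ q × D.

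- q is the share of alirocumab values at a time point that are missing more than 21 days into a gap. The documents do not give it. The range 0.5–3% is an assumption.
- D is the on-drug difference from placebo. Protocol section 4 reports Phase 2 differences of 57.3 and 67.3 percentage points at 150 mg every 2 weeks. They come from other populations, and this trial starts every alirocumab patient at 75 mg, so they serve only as a scale.

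Results:

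- q = 0.5%: 0.005 × 57.3 = 0.29; 0.005 × 67.3 = 0.34
- q = 1%: 0.01 × 57.3 = 0.57; 0.01 × 67.3 = 0.67
- q = 3%: 0.03 × 57.3 = 1.72; 0.03 × 67.3 = 2.02

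The range is about 0.3–2.0 percentage points. This assumes that the whole effect is lost in the gap and that imputation restores all of it. If half the effect persists, the range halves to about 0.14–1.01 points. It shrinks further because values observed in gaps count as on-treatment measurements and so feed the imputation model.

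**The case against.** The case for leaving the rule alone has several parts.

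- **Appendix F may settle it.** It holds the detailed pattern-mixture method and could treat interruptions separately. This stands as a condition on the point.
- **Few values are exposed.** Protocol 10.3 asks that visits and assessments carry on during an interruption, and the ITT analysis uses observed values as they are (SAP 3.4.7.4). A patient must be more than 21 days into a gap and also lack a usable sample. This stands, and it limits the size.
- **The consequences are limited.** SAP 3.1.5 calls these endpoints exploratory, and 3.4.7.4.1 makes their p-values descriptive. They lie outside the testing hierarchy. This also stands.
- **The net direction is not established.** A reader might infer that the ITT lipid effect as a whole is overstated. SAP 3.1.4 expects residual effect up to 10 weeks after the last dose, yet 3.4.7.4.1 imputes from baseline once 21 days have passed. For permanent discontinuers that works against alirocumab. Only the direction for values missing in gaps can be stated.
- **The labels are defensible.** A reader might infer that neither lipid analysis is what its name says. For the ITT analysis that is wrong: it uses all observed values whether or not the patient is on therapy. The on-treatment analysis is defined openly by its period. Off-drug values observed in gaps would dilute its estimate, which is conservative. Removing them would select on adherence and change the estimand.

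None of this explains why a missing value on day 60 of a gap should be imputed as on-drug on the strength of a 21-day argument.

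**Conclusion.** The point holds for missing lipid values only. The imputation rule is inconsistent with its own rationale during interruptions longer than 21 days, and for those values the bias favours alirocumab. The illustrative upper bound of 0.3–2.0 percentage points rests on an assumed 0.5–3% share and on borrowed Phase 2 effects. Against a difference of 57–67 points it would not change a conclusion about LDL-C lowering. The primary and main secondary time-to-event analyses are untouched. The case for changing the rule is that it is directional, depends on what happens after the time point, and is cheap to remove. The conclusion assumes that Appendix F contains no separate rule for gaps.

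**What to change.** First check Appendix F. If it has no rule for interruptions, amend SAP 3.4.7.4.1 so that each missing lipid time point, in both arms, is classified by days since the most recent double-blind injection as SAP 3.1.4 defines it:

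- up to 21 days: missing at random, imputed from on-treatment measurements;
- more than 21 days: the baseline-based imputation already used after discontinuation.

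State whether this carries over to lipoprotein(a) and triglycerides in 3.4.7.4.2, which reuse these imputations. Keep the on-treatment repeated-measures model as defined. Optionally add a sensitivity analysis that excludes values taken more than 21 days after the most recent injection.

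The cost is a change of wording and one derived flag. Injection data already reach the eCRF through the diary and treatment log (Protocol 8.7.1). The drawback is a hard cut at 21 days that ignores residual effect: after one omitted injection, days 22–28 would be imputed from baseline. The SAP already accepts that simplification after the final injection.

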#### **11.4.2.2 Analyses of secondary efficacy endpoints**

Method for controlling the overall Type-I error rate when testing the key secondary efficacy endpoints is described in [Section 11.4.2.3](#).

Time to events secondary endpoints will be analyzed using the same statistical methodology as for the primary endpoint.

The percent change from baseline in calculated LDL-C at Month 4, at Month 24 and at the end of the study will be analyzed in the ITT population using an analysis of covariance (ANCOVA) model with treatment group and region as fixed effects, and the baseline calculated LDL-C as covariate.

Similar analyses will be performed for ApoB and non-HDL.

Based on previous experiences and published data on these endpoints, the assumptions of normality of the residuals, homogeneity of slopes and homoscedasticity underlying these models are usually valid.

Throughout the ANCOVA models, the alirocumab group will be compared to placebo using an appropriate contrast tested at the two-sided 0.05 level, and providing the 95% confidence interval (CI) of the difference.

For patients without calculated LDL-C, ApoB, or non-HDL-C value in the time window analyzed, the percent change from baseline will not be calculated.

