2.2 STATISTICAL MODIFICATIONS MADE IN THE STATISTICAL ANALYSIS PLAN

The statistical analysis plan history table below gives the timing, rationale, and key details for major changes to the statistical analysis features

- in the first version of the statistical analysis plan dated on 25 January 2016 compared to the protocol amendment 8 (version currently in effect at this time)
- in the amended versions of the statistical analysis plan (versions 2 and 3) compared to the first version of 25 January 2016.

Changes already incorporated in a protocol amendment are listed only in Table 2.

With regard to the study timelines, the first patient was enrolled on 02 November 2012. The first interim analysis occurred in April 2016 with the data cut-off for the interim analysis on 30 November 2015. The second interim analysis occurred when approximately 1210 patients had at least one positively-adjudicated primary efficacy endpoint, with review of the data by the DMC in November 2016.

SAP			
version	Date		
number	approved	Rationale	Description of statistical changes
1	25-Jan-2016	Imputation method not planned for missing lipid values	For patients without lipid values in the time window analyzed, multiple imputation will be used with different imputation strategies depending on the time of those missing values (during the treatment period or after treatment discontinuation) (see Section 3.4.7.4.1)
1	25-Jan-2016	End of analysis period for the analysis of TEAEs for patients with 2 consecutives low LDL-C did not take into account down-titrations from 150 mg to 75 mg	In the specific analysis of TEAEs for the subgroup of patients with two consecutive LDL-C <25 mg/dL (respectively 15 mg/dL) within the alirocumab treatment group, the upper limit of the analysis period for patients down-titrated from 150 mg to 75 mg will end at the date of last injection of 150 mg +70 days (see Section 3.4.5.1).
1	25-Jan-2016	Selection of patients with 2 consecutive LDL-C <25 mg/dL (respectively 15 mg/dL) modified consistently with the other studies of the program.	The patients will be considered as having 2 consecutive LDL-C <25 mg/dL (respectively 15 mg/dL) if these values are spaced out by at least 21 days (see Section 3.1.5.4).

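### The SAP's ITT lipid ANCOVA leaves out the region effect that the protocol specifies for LDL-C, ApoB and non-HDL-C, and the change tables do not record it

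*SAP*

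**What the plan says.** Protocol 11.4.2.2 analyses percent change from baseline in calculated LDL-C at Month 4, Month 24 and the end of the study by an ANCOVA "model with treatment group and region as fixed effects, and the baseline calculated LDL-C as covariate". It then adds: "Similar analyses will be performed for ApoB and non-HDL".

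SAP 3.4.7.4.1 (ITT analyses of lipid parameters) analyses the multiply imputed data sets by ANCOVA, or by robust regression for triglycerides and Lp(a). Both models are stated "with treatment group as fixed effect, and the baseline lipid value as continuous covariate". Region does not appear.

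SAP 3.4.7.4.2 adds an on-treatment mixed model for repeated measures: "The model will include the fixed categorical effects of treatment group (placebo, alirocumab), planned time point (Month 1 to Month 64), treatment-by-time point interaction". Its remaining terms are baseline and baseline by time point. It has no region term either.

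SAP 2.2 introduces Table 3 as a history that "gives the timing, rationale, and key details for major changes to the statistical analysis features", comparing SAP version 1 with protocol amendment 8 and later SAP versions with version 1. The only row that points to 3.4.7.4.1 has the rationale "Imputation method not planned for missing lipid values". Table 2, on protocol amendments, says nothing about the lipid model.

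**The concern.** For three lipid parameters the protocol names an adjustment that the SAP omits without giving a reason. Region is a natural term to keep. Randomization is stratified by country, and SAP 3.4.4.1 groups countries into regions because events per country will be few, so region stands in for the stratification factor at the analysis stage. When an analysis ignores a stratification factor that predicts the outcome, the treatment estimate still benefits from the balance, but the model standard error takes no credit for it and comes out too wide.

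Two things are at stake, both small: agreement between protocol and SAP on a stated secondary objective (the effect on LDL-C, ApoB and non-HDL-C), and slightly wide confidence intervals.

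**Working it through.** **Text comparison.**
- Protocol 11.4.2.2, LDL-C (ApoB and non-HDL-C similarly): treatment, region, baseline.
- SAP 3.4.7.4.1, ANCOVA: treatment, baseline.
- SAP Tables 2 and 3: no entry on region in the lipid model.
- Dates: SAP version 1 is 25-Jan-2016, the supplied protocol (amendment 11) is 25-Feb-2016 and still has region, and the supplied SAP (version 3) is 11-Oct-2017 and does not.

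**Size.** The plan gives no power or precision figure for the lipid models, so there is none to reproduce. It gives neither a residual SD nor the share of variance due to region. The values below are assumptions: SD 30 or 40 percentage points, R² (share of residual variance explained by region) 1%, 3% or 5%, and 9,000 patients per arm with values.

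Without region, SE of the difference = SD × √(2/9000). For SD 30 this is 30 × 0.01491 = 0.447, and for SD 40 it is 40 × 0.01491 = 0.596. With region, the SE is multiplied by √(1 − R²):

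| R² | Factor | SE, SD 30 | SE, SD 40 |
|---|---|---|---|
| 0 | 1 | 0.447 | 0.596 |
| 1% | 0.995 | 0.445 | 0.593 |
| 3% | 0.985 | 0.440 | 0.587 |
| 5% | 0.975 | 0.436 | 0.581 |

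The reduction is 0.5%, 1.5% or 2.5%. At SD 30 and R² = 5%, the 95% half-width goes from 1.96 × 0.447 = 0.88 to 1.96 × 0.436 = 0.85 percentage points. The factor does not depend on the SD or the number of patients.

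**Cost of the term.** Six levels add five parameters. With 18,000 patients the effect on the SE is √(17,997/17,992) = 1.0001.

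**Bias and error rate.** These were checked by simulation under no treatment effect: about 6,000 patients, 50 countries in six regions, permuted blocks of four within country (block size assumed), R² of 1%, 5% and 10%, and 1,200 runs each.
- The mean estimate was within 0.0004 SD of zero in both models.
- In no run did the two estimates differ by more than 0.0024 SD.
- Rejection at two-sided 5% was 0.034 to 0.046 without region and 0.038 to 0.046 with it. The Monte Carlo standard error is √(0.05 × 0.95/1200) = 0.006.
- At R² = 5% the actual spread of the estimates was the same (0.0245 in both models), while the average model SE was 0.0259 without region and 0.0252 with it.

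Stratified randomization has therefore already secured the precision. What the omission changes is the reported standard error, on the conservative side.

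**The case against.** The strongest reply is that nothing depends on this. SAP 3.1.5 calls these endpoints exploratory, 3.4.7.4.1 makes the lipid p-values descriptive, and they lie outside the testing hierarchy. Table 3 is confined to major changes, and a shift of at most a few percent in a standard error is hardly major. The amendment 8 text, against which SAP version 1 was compared, is not among the supplied documents. SAP 3.5.6 also limits the pooling into regions to describing the population, the primary efficacy analysis and the subgroup analyses, so the lipid models fit the SAP's own stated scope.

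Most of this stands, and it sets the weight of the point. It does not remove the mismatch: the later protocol still has region. Table 3 also records finer matters, such as a 21-day spacing rule for two low LDL-C values and a one-day change in an imputed injection date.

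Some stronger readings are tempting, but the documents do not support them:
- A reader might infer that the SAP contradicts itself because it uses region in every time-to-event model. It does not. Region is in the primary log-rank and Cox analyses, the secondary endpoints that follow them, and the main subgroup models. No region term is stated for the Cox model with continuous time from ACS (3.4.4.1), nor for the adverse-event and low-LDL-C Cox models (3.4.5.1).
- A reader might infer that region was also removed from the robust regression and the on-treatment mixed model. Protocol 11.4.2.2 contains neither; they are SAP additions.
- A reader might expect more benefit for HDL-C, triglycerides and Lp(a), where effects are smaller. The factor √(1 − R²) does not involve the effect size, and no R² is given for any lipid.
- A reader might suspect that the imputation model omits region too. That model is detailed in Appendix F, which is not supplied, so this cannot be judged.

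**Conclusion.** The point holds as a minor one. For LDL-C, ApoB and non-HDL-C the SAP's ITT ANCOVA lacks a fixed effect that the protocol specifies, and the change tables neither log nor explain it. The consequence is a model standard error that including region would lower by about 0.5% to 2.5%.

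That range rests on the assumed 1% to 5% share of residual variance. The absolute figures also assume an SD of 30 to 40 points and 9,000 observed values per arm, and they ignore the variance added by multiple imputation.

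A reader might go further and infer a biased comparison or an inflated error rate. The check shows neither. No confirmatory conclusion changes.

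**What to change.** Before unblinding, amend SAP 3.4.7.4.1 so that the ANCOVA for LDL-C, ApoB and non-HDL-C has treatment group and region (the six levels of Table 9) as fixed effects and the baseline value as covariate, as protocol 11.4.2.2 states. Add the lipid ANCOVA to the uses of region listed in 3.5.6, and add a row to Table 3. If the sponsor prefers the model without region, that row should give the reason.

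One sentence in 3.4.7.4.1 covers all the ANCOVA parameters and the robust regression, so it may be simpler to put region in throughout, and in the on-treatment mixed model. That is optional and for consistency only, because the protocol did not specify region there.

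The cost is a clause in the SAP, one term in the programs and five degrees of freedom. No new data are needed.
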